13.8.3 Leukemia Blasts

The analyses for changes in expression of co-signaling molecules on leukemia blasts (CD10⁺/CD19⁺/CD34⁺) before and after treatment with blinatumomab and checkpoint inhibitors will be summarized using descriptive statistics and either Wilcoxon rank sum tests or paired t tests, as appropriate for a single time point, or using the mixed effects linear regression models for simultaneously modelling data from multiple time points as previously described for analyzing the T cell population data. We will explore the changes in blasts in terms of expression of co-signaling molecules over time and summarize any correlation in the pattern of blast changes over time using the regression models and interaction tests described above.

13.8.4 Cytokine Profiling

Changes in cytokine levels for all patients and within patient subgroups will be summarized using descriptive statistics and either Wilcoxon rank sum tests or paired t tests, as appropriate for a single time point, or using the mixed effects linear regression models previously described for simultaneously modelling data from multiple time points for the T cell population data.

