2.4.4 Cytokine studies

Blinatumomab treatment has been associated with transient release of cytokines such as IL-2, IL-6, IL-10, IFN- γ and TNF- α . However, there was not a clear pattern of cytokine release and response.⁸² Administration of novel immunotherapeutics, including immune checkpoint inhibitors, alone or in combination with chemotherapy have resulted in systemic immune-related AEs.⁹⁰ Whether administration of nivolumab and nivolumab/ipilimumab following blinatumomab will increase cytokine expression and if increases in cytokines will be associated with toxicity is unknown. Thus, we will be collecting and storing serial plasma samples (at the time of PB collection) and if there is a strong rationale we will conduct measurement of cytokines to assess blinatumomab and checkpoint inhibitors-induced global T-cell activation. We will examine the levels of cytokines before and after treatment with blinatumomab and checkpoint inhibitors, including the levels of sCTLA-4. In particular, sCTLA-4 is found at a significantly higher frequency in ALL patients than healthy controls, and higher levels of sCTLA-4 correlate with relapse risk and the probability of survival following treatment.^{77,78} Experimental evidence suggests that current anti-CTLA-4 antibodies bind both sCTLA-4 and membrane-bound CTLA-4 and as such that their administration may improve the immune recognition of ALL cells.⁷⁹ We anticipate that the levels of sCTLA-4 may decrease upon ipilimumab treatment.

2.4.5 **Immune profiling of T cell repertoire and characterize T cell transcriptional signature before and after treatment**

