9.2.1.2 **Exploratory/ Ancillary Correlative Laboratory Studies #2: Characterize the expression of co-signaling molecules on BM or PB ALL blasts prior to, during and after blinatumomab and checkpoint inhibition (Pre-treatment, week 2 Cycle 1 if feasible, at response assessment following Cycle 1 and/or 2, BM).** Flow cytometric studies will be performed on leukemia blasts (CD19/CD10/CD34 plus other leukemia specific marker) to examine for expression of co-stimulatory and co-inhibitory molecules such as PD-L1, B7-H3, VISTA, Gal-9, CD86, PVR, PVR2, OX40L, ICOSL at baseline, within 10 days of blinatumomab treatment (prior to first administration of checkpoint inhibitors), in non-responders following combination treatment after cycle 1 and/or 2, and at the time of relapse. Collected specimens will also serve to examine for other mechanisms of relapse or resistance such as CD19 loss.

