13.5 Sample Size/Accrual Rate

In the dose escalation phase of this study, the sample size is determined by the number of DLTs observed. The minimum sample size for this first part of the study will be 6 patients at DL1 and DL-1 (if necessary), and a maximum sample size of 12 patients. During the dose escalation phase of the combination arm, the minimum number of patients treated will be 3 and maximum will be 6 at each dose level. If the combination is deemed safe and the expansion cohort is enrolled, the sample size will be either 9 or 12 at that dose level. The maximum total sample for the entire study will be 36 patients.

The anticipated complete response (CR) rate in this patient population is approximately 40%. With a minimum sample size of 12 subjects in the combination arm, the probabilities of observing at least 5 responses out of 12 patients (41.7% CR rate) would be 0.42, 0.56, and 0.70 if the true CR rate is 35%, 40%, and 45%, respectively. If the true CR rate is less than 15%, the chance of observing 5 responses out of 12 would be 0.024 or less. This sample size also allows for estimation of the CR rate with precision (half the width of the 95% exact binomial confidence interval) being no wider than 25.5%.

PLANNED ENROLLMENT REPORT

Racial Categories	Ethnic Categories				Total
	Not Hispanic or Latino		Hispanic or Latino		
	Female	Male	Female	Male	
American Indian/ Alaska Native	0	0	0	0	0
Asian	1	0	0	0	1
Native Hawaiian or Other Pacific Islander	0	0	0	0	0
Black or African American	1	2	0	0	3
White	7	13	3	3	26
More Than One Race	0	0	0	0	0
Total	9	15	3	3	30

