13.8 Analysis of Exploratory Endpoints

13.8.1 Characterizing T cell populations

The analyses of pre- and post-treatment PB and BM specimens for immune parameters will be descriptive and graphical in nature. Data will be summarized for each patient group separately (blinatumomab plus nivolumab; blinatumomab plus nivolumab and ipilimumab). Flow values at each time point will be summarized using geometric means and standard deviation. Differences in baseline values between patient subgroups will be explored using linear regression models. We are specifically interested in determining what pretreatment signature is associated with outcome, such as having a complete response or becoming refractory. To this end, we will use logistic regression models with ROC analysis to describe which pretreatment parameters are potential predictors of outcomes following treatment. Values will be checked for skewness and log-transformed as appropriate. The change in flow values at each time point after blinatumomab and blinatumomab plus checkpoint inhibitor(s) relative to the baseline value will be modeled using mixed-effects, linear regression models that include fixed effects for time point and a random effect for the patient to account for within-patient correlation of measurements. Post-treatment changes in T cell populations will be correlated with clinical outcomes such as CR vs. No CR or MRD vs. No MRD using interaction tests. T cell subsets in the PB and BM defined by multicolor flow cytometry will be summarized before and after treatment with blinatumomab alone or plus checkpoint inhibitors by treatment group using summary statistics. Differences in T cells before and after treatment will be explored using non-parametric Wilcoxon signed rank tests or paired t tests as appropriate. The expression of co-inhibitory/-stimulatory molecules will also be examined in the same way.

13.8.2 Characterization of T cell transcriptional signature before and after treatment.

Expression levels will be summarized at pre-treatment and post-treatment using standard descriptive statistics. Differentially-expressed genes and corresponding fold-changes will be analyzed using standard statistics and through the use of Ingenuity pathway analysis as described previously. We will identify differentially-expressed genes by patient subgroups such as CR v. NR and MRD v. No MRD using interaction tests.

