6. Clinical utility of the integrated assay: Flow values at each time point will be summarized using geometric means and standard deviation. Differences in baseline values between patient subgroups will be explored using linear regression models. We are specifically interested in determining what pretreatment signature is associated with outcome, such as having a complete response or becoming refractory. To this end, we will use logistic regression models with ROC analysis to describe which pretreatment parameters are potential predictors of outcomes following treatment. Values will be checked for skewness and log-transformed as appropriate. The change in flow values at each time point after blinatumomab and blinatumomab plus checkpoint inhibitor(s) relative to the baseline value will be modeled using mixed-effects, linear regression models that include fixed effects for time point and a random effect for the patient to account for within-patient correlation of measurements. Post-treatment changes in T cell populations will be correlated with clinical outcomes such as CR vs. No CR or MRD vs. No MRD using interaction tests. T cell subsets in the PB and BM defined by multicolor flow cytometry will be summarized before and after treatment with blinatumomab alone or plus checkpoint inhibitors by treatment group using summary statistics. Differences in T cells before and after treatment will be explored using non-parametric Wilcoxon signed rank tests or paired t tests as appropriate. The expression of co-inhibitory/-stimulatory molecules will also be examined in the same way.

References:

[figure not shown]

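### Sections 13.8.3 and 13.8.4 name the Wilcoxon rank sum test, an independent-samples test, for within-patient change; 13.8.1 and Appendix C name the signed rank test for the parallel comparison

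*Combined protocol and SAP*

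**What the plan says.** Section 13.8.3 (leukemia blasts) covers changes in co-signaling molecule expression before and after treatment. Section 13.8.4 covers cytokines: "Changes in cytokine levels for all patients and within patient subgroups will be summarized using descriptive statistics". Both then give the same pair of tests: "either Wilcoxon rank sum tests or paired t tests, as appropriate for a single time point". Data from several time points go to the mixed-effects models of 13.8.1, which "include fixed effects for time point and a random effect for the patient to account for within-patient correlation of measurements".

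Section 13.8.1 makes the parallel before/after comparison for T cells, and there the differences "will be explored using non-parametric Wilcoxon signed rank tests or paired t tests as appropriate". Appendix C (item 6, clinical utility of the assay) repeats this: "Differences in T cells before and after treatment will be explored using non-parametric Wilcoxon signed rank tests", again with the paired t test as the alternative.

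**The concern.** The rank sum (Mann-Whitney) test compares two independent samples. The nonparametric counterpart of the paired t test is the signed rank test. The single-time-point sentence in 13.8.3 and 13.8.4 therefore joins two tests that answer different designs. A set of within-patient changes is one sample, so the rank sum test can be run on it only by splitting the baseline and follow-up values into two groups and discarding the link between them.

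An analyst who follows the text literally would use this option when the changes look non-normal, which is when a nonparametric test would be chosen. With positively correlated pre and post values, real changes in resistance markers or cytokines could be missed in a small study.

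**Working it through.** **Comparing the sections**

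| Place | Quantity | Nonparametric option | Parametric option |
|---|---|---|---|
| 13.8.1 | T cells before vs after | signed rank | paired t |
| Appendix C, item 6 | T cells before vs after | signed rank | paired t |
| 13.8.3 | change in blast markers | rank sum | paired t |
| 13.8.4 | change in cytokines | rank sum | paired t |

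The parametric option is paired in all four places. The mixed model that 13.8.3 and 13.8.4 refer back to carries a patient random effect. The plan therefore treats these data as paired everywhere except in the rank sum option.

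**Inputs for the illustration**

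The documents give no power, alpha, effect size or correlation for these endpoints, so there is no stated figure to reproduce.

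- From 13.5: 12 pairs (one dose level with its expansion cohort), 30 pairs (planned enrollment total) and 36 pairs ("The maximum total sample for the entire study will be 36 patients").
- Assumed: bivariate normal values with unit SD, shift 0.6 SD, two-sided 5%, correlation ρ = 0, 0.3, 0.5 or 0.7.
- Method: exact tests on 20,000 simulated data sets per setting.

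**Power, signed rank vs rank sum**

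| Pairs | ρ = 0 | ρ = 0.3 | ρ = 0.5 | ρ = 0.7 |
|---|---|---|---|---|
| 12 | 23% vs 26% | 32% vs 23% | 43% vs 21% | 64% vs 17% |
| 30 | 59% vs 61% | 75% vs 63% | 88% vs 65% | 98% vs 69% |
| 36 | 68% vs 69% | 83% vs 72% | 93% vs 75% | 99% vs 80% |

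At ρ = 0.5 the loss is 43 − 21 = 22, 88 − 65 = 23 and 93 − 75 = 18 percentage points.

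**Actual size of the rank sum test (nominal 5%)**

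| Pairs | ρ = 0 | ρ = 0.3 | ρ = 0.5 | ρ = 0.7 |
|---|---|---|---|---|
| 12 | 4.4% | 2.0% | 0.8% | 0.2% |
| 30 | 4.8% | 2.2% | 0.7% | 0.1% |
| 36 | 4.8% | 2.0% | 0.6% | 0.1% |

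The signed rank test's size stays at 4.0–4.3% (12 pairs), 4.8–5.3% (30) and 4.9–5.2% (36).

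**Check by formula**

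In large samples, pairing multiplies the null variance of the rank sum statistic by about 1 − ρₛ, where ρₛ = (6/π)·arcsin(ρ/2) is the rank correlation for normal data. The test still uses the independent-samples variance, so its size is about 2Φ(−1.96/√(1 − ρₛ)).

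- ρ = 0.3: ρₛ = 0.288; 1.96/√0.712 = 2.32; size about 2.0%.
- ρ = 0.5: ρₛ = 0.483; 1.96/√0.517 = 2.72; size about 0.6%.
- ρ = 0.7: ρₛ = 0.683; 1.96/√0.317 = 3.48; size about 0.05%.

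These agree with the simulated sizes, most closely at 36 pairs.

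**The case against.** **A between-group reading.** A rank sum test could validly compare changes between independent subgroups, such as CR against no CR. The text does not support this reading. Section 13.8.4 speaks of change within subgroups, the parametric partner is a paired rather than a two-sample t test, and differences in change by outcome go to interaction tests.

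**The illustration is generous for blasts.** This stands. Under 9.2.1.2, blasts are studied "at baseline, within 10 days of blinatumomab treatment (prior to first administration of checkpoint inhibitors", and after combination treatment only in non-responders and at relapse. Section 5.2.1 reports complete remission in 5 of 6 patients at dose level A1. Post-combination blast pairs will therefore be few, and 30 or 36 pairs fits cytokines or, at most, the early baseline-to-day-10 blast comparison. With the same assumptions and ρ = 0.5, power for signed rank vs rank sum is about 15–16% vs 8–10% with 6 pairs and 25–26% vs 14% with 8. With 5 or fewer pairs the exact two-sided signed rank test cannot reach 5%, because its smallest p-value is 2/2⁵ = 0.0625. Both tests are then weak, but that does not justify the rank sum test.

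**Normal data.** The simulation uses normal values, for which the valid paired t test would be expected (power 48%, 89% and 94% at ρ = 0.5 with 12, 30 and 36 pairs). No figures for skewed data are given. This limits the magnitude but does not change which test is correct.

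**Other routes exist.** The paired t test and the mixed models are valid, and because sampling is serial the models may carry much of the analysis. Section 13.8.1 also calls these analyses descriptive and adds that co-signaling molecule expression will be handled like the T cells, which supports reading this as a slip.

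**Cytokines may not be measured.** Section 2.4.4 says "if there is a strong rationale we will conduct measurement of cytokines", but 9.2.2.1 and 13.3.3.4 state the measurement without that condition, so it cannot be relied on to make the point moot.

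**Conclusion.** The concern holds, at minor severity. The rank sum option in 13.8.3 and 13.8.4 is the wrong test for within-patient change and conflicts with 13.8.1 and Appendix C.

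If it were used, and pre and post values correlated positively, the consequence would be lost sensitivity rather than extra false positives. The size of the loss depends on the assumed shift, correlation and alpha: roughly 20 percentage points of power at correlation 0.5 with 12 to 36 pairs, about 6 to 12 points with 6 to 8 pairs, and none at zero correlation.

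The effect is confined to the single-time-point nonparametric option under exploratory objectives 1.3.3 and 1.3.4. No primary or secondary result, DLT or MTD decision, or stopping rule depends on it.

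**What to change.** In 13.8.3 and 13.8.4, replace the Wilcoxon rank sum test with the Wilcoxon signed rank test for within-patient change, matching 13.8.1 and Appendix C. Keep the rank sum test only where changes are compared between independent subgroups. If such a comparison is intended, say so explicitly and pair it with a two-sample t test. The cost is one test name corrected in two sections, with no new data, samples or analyses.

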13.8.5 Immune Profiling

Immune profiling of T cell repertoire and characterize T cell transcriptional signature before and after treatment will be analyzed using the approach outlined in a prior study.⁹⁹ Specifically, two distinct measures, clonality and Gini coefficient, will assess the degree of clonal skewing in the *TRB* repertoires. Clonality is a metric derived from the Shannon entropy of the frequency distribution of *TRB* sequences normalized by the $\log_2(\text{number of unique } TRB \text{ sequences})$; it captures the clonal composition of a T cell population and has an adjustment for sequencing depth, thus making it less sensitive to this critical variable.¹⁰³ The Gini coefficient is a graphically defined metric of repertoire diversity in the sequence frequency distribution. These measures will be used to define clonality, which will be correlated with patient outcomes, such as CR v No CR and MRD v No MRD.

REFERENCES

APPENDIX A: PERFORMANCE STATUS CRITERIA

ECOG Performance Status Scale		Karnofsky Performance Scale	
Grade	Descriptions	Percent	Description
0	Normal activity. Fully active, able to carry on all pre-disease performance without restriction.	100	Normal, no complaints, no evidence of disease.
		90	Able to carry on normal activity; minor signs or symptoms of disease.
1	Symptoms, but ambulatory. Restricted in physically strenuous activity, but ambulatory and able to carry out work of a light or sedentary nature (e.g., light housework, office work).	80	Normal activity with effort; some signs or symptoms of disease.
		70	Cares for self, unable to carry on normal activity or to do active work.
2	In bed <50% of the time. Ambulatory and capable of all self-care, but unable to carry out any work activities. Up and about more than 50% of waking hours.	60	Requires occasional assistance, but is able to care for most of his/her needs.
		50	Requires considerable assistance and frequent medical care.
3	In bed >50% of the time. Capable of only limited self-care, confined to bed or chair more than 50% of waking hours.	40	Disabled, requires special care and assistance.
		30	Severely disabled, hospitalization indicated. Death not imminent.
4	100% bedridden. Completely disabled. Cannot carry on any self-care. Totally confined to bed or chair.	20	Very sick, hospitalization indicated. Death not imminent.
		10	Moribund, fatal processes progressing rapidly.
5	Dead.	0	Dead.

APPENDIX C: BIOASSAY TEMPLATES

Exploratory/Ancillary Biomarkers for the Assessment of T-cell Subset Distribution, Differentiation Status, and the Expression of Co-signaling molecules and Canonic Transcription Factors in both the peripheral blood and bone marrow microenvironment

1) **Name of Marker:** Surface expression of cluster of differentiation (CD) markers and intracellular transcription factors in peripheral blood and bone marrow T cells

2) **Role of the Biomarker Assay in the Trial: Exploratory Assay.**

➤ **Assay purpose:**

- a) To determine phenotypic correlates of effective response to blinatumomab and checkpoint inhibitors (nivolumab with or without ipilimumab)
- b) To assess phenotypic predictors of responsiveness to blinatumomab and checkpoint inhibitors (nivolumab with or without ipilimumab)
- c) To determine which T cell populations are the targets of checkpoint inhibitors in combination with blinatumomab

➤ **Assay type:** Flow cytometry.

3) **Laboratory conducting study for the trial:** [name] research laboratory.

4) **Assay:** Standardized tubes and procedures will be used for specimen collection, processing, cryopreservation and storage (Appendix E). Our workflow has been specifically designed to maximize information yield from smaller samples and is based on well developed and implemented standard operating procedures (SOPs). In our analysis we will utilize standardized pre-determined multi parametric flow-cytometry mAb panels that interrogate dynamic changes across comprehensive immune cell populations. In the development and use of the integrated biomarker assay in the context of clinical trial we have followed guidelines from the Biomarkers Taskforce of the NCI Investigational Drug Steering Committee (*Dancey JE et al. Clin Cancer Res 2010;16:1745-55*). We will also follow all recommendations and protocols for standardizing immunologic readouts such as published by SITC/FDA/NCI Workshop on Immunotherapy Biomarkers (*Butterfield LH et al. Clin Cancer Res 2011;17(10):3064-76*). All multicolor flow-cytometry panels will follow standard principles of panel design and follow recommendation published by the "Human Immune Phenotyping Consortium" on the standardization of flow cytometry immunophenotyping in clinical studies (*Maecker HT et al. Nat Rev Immunol 2012, 12:191-200*).

- **Analyte(s) and sources of assay components:** The directly conjugated monoclonal antibodies outlined in the Table 1 below. All antibodies will be obtained from commercial vendors.

Table. 1

Antigen	Fluorochrome	Clone	Antibody type	Cat No.	Company
CD3	AF700	HIT3a	Mouse IgG2a, κ	300324	BioLegend
CD3	APC	OKT3	Mouse IgG2a, κ	17-0037-42	eBioscience
CD3	evolve 605	OKT3	Mouse IgG2a, κ	83-0037-42	eBioscience
CD4	PerCP Cy5.5	OKT4	Mouse IgG2b, κ	45-0048-42	eBioscience
CD4	BV605	OKT4	Mouse IgG2b, κ	317438	Biolegend
CD8	PerCP-Cy5.5	RPA-T8	Mouse IgG ₁ , κ	45-0088-42	eBioscience
CD8	pacorange	3B5	Mouse IgG2a	MHCD0830	Thermo Fisher (Invitrogen)
CD45RA	APC-Cy7	HI100	Mouse IgG2b, κ	304128	BioLegend
CCR7	BV650	G043H7	Mouse IgG2a, κ	353234	BioLegend
CD25	PE-Cy7	BC96	Mouse IgG ₁ , κ	302612	BioLegend
CD27	BV605	O323	Mouse IgG1, κ	302830	BioLegend
CD27	AF700	M-T271	Mouse IgG1, κ	560611	BD
CD28	PE-Cy7	CD28.2	Mouse IgG1, κ	25-0289-42	eBioscience
CD127	e-fluor 450	eBioRDR5	Mouse IgG ₁ , κ	48-1278-42	eBioscience
BTLA (CD272)	AF647	MIH26	Mouse IgG2a, κ	344510	Biolegend
BTLA (CD272)	PE	MIH26	Mouse IgG2a, κ	344506	Biolegend
CD160	AF488	BY55	Mouse IgM	53-1609-42	eBioscience
CD244 (2B4)	FITC	C1.7	Mouse IgG ₁ , κ	329506	Biolegend
CD57	pacblue	HCD57	Mouse IgM, κ	322316	BioLegend
KLRG1	APC	REA261	Mouse IgG ₁ , κ	130-103-639	Miltenyi
CTLA-4 (CD152)	AF647	BNI3	Mouse IgG2a, κ	555855	BD
PD1 (CD279)	PE	EH12.1	Mouse IgG ₁ , κ	560795	BD
TIM3 (CD366)	PE	344823	Rat IgG2A	FAB2365P	R&D Systems
PDL1	Alexa Fluor 700	MIH1	Mouse IgG ₁ , κ	565188	BD
CD56	PECF594	B159	Mouse IgG ₁ , κ	562289	eBioscience
Ki-67	PerCP Cy5.5	B56	Mouse IgG ₁ , κ	561284	BD
CD69	PE	FN50	Mouse IgG1, κ	12-0699-42	eBioscience
T-bet	PE-CF594	04-46	Mouse IgG ₁ , κ	562467	BD
FoxP3	V450	259D/C7	Mouse IgG ₁ , κ	560459	BD
HLA-DR	FITC	G46-6	Mouse IgG2a, κ	555811	BD
TNFR2 (CD120b)	PE	3G7A02	Rat IgG2a, κ	358404	Biolegend
LAG-3 (CD223)	PE-Cy7	3DS223H	Mouse IgG1, κ	25-2239-42	eBioscience
Eomes	PE	WD1928	Mouse IgG1, κ	12-4877-42	eBioscience
Blimp-1	PE-CF594	6D3	Rat IgG2a, κ	565274	BD
CD16	PerCP Cy5.5	3G8	Mouse IgG ₁ , κ	302028	Biolegend
CD95	Pacific Blue (V450)	DX2	Mouse IgG ₁ , κ	305619	Biolegend
LIVE/Dead fixable Aqua Dead stain kit	405 nm			L34957	Life Technologies

- **Technical platform:** The Cancer Center flow cytometry facility is equipped with two Becton Dickinson (BD) FACS Aria II cell sorters, a BD LSR Fortessa with capability of simultaneous analysis of up to 18 colors, and a BD LSR II with capability of simultaneous analysis of up to 15 colors are available for use in this project.
- **Specimens:** Peripheral blood samples will be obtained via phlebotomy while bone marrow will be collected through standard access to iliac crest. Peripheral blood should be drawn in 4-10 ml green-top vacutainer tube (sodium heparin) as per schedule defined in the protocol Section 9.1 and the Study Calendar (Table 10.1). Aspirated bone marrow cells will be collected in a 4-10 ml green-top vacutainer tube (sodium heparin). All collected specimens will be labeled with the patient's study number, sample collection date and time, and sample source (PB or BM). Specimen collection will be recorded on Correlative Studies Collection Worksheet (Appendix F). All data should be kept in laboratory log.
- **Anticipated methods for specimen processing:** At each sampling interval, BM and PB mononuclear cells (PBMC) will be processed by Ficoll density gradient centrifugation. Please refer to Appendix E: Protocol for Plasma/PBMC isolation (Ficoll Hypaque). Each sample is aliquoted in multiple vials of 5-20 x 10⁶ cells/vial for PBMC and 25-75 x 10⁶ for BM samples. This strategy for sample processing enables purification of PBMCs and the corresponding mononuclear cell fraction from BM, and of plasma, for separate experimental uses. Freezing enables sample collection over time, which allows analysis of multiple samples simultaneously in a single experiment (batching) for increased reproducibility and comparability of results. The cell viability upon freeze and subsequent thaw is >85% for the majority of the samples (lower viability can be seen in samples from patients with uncontrolled leukemia). The function and numbers of the lymphocyte populations of interest have been found to be mostly unaffected by freezing and thawing in recent study (small changes in the numbers of CD8⁺ T cells, naïve T cells and central memory T cells have been described, but are generally assessed as being of minor importance) (Riedhammer *et al. Methods in Molecular Biology* 2015; 1304: 53–61). Thawed cells will be washed in phosphate-buffered saline (PBS) before staining with appropriate concentrations of fluorochrome-conjugated monoclonal antibodies. We are also routinely allowing a short rest period before staining and closely follow the literature on optimal use of the markers on cryoprocessed specimens (Ogunjimi *B et al. J Immunol Methods* 2013;392:63-67; Lemieux *J et al. J Immunol Methods* 2016;434:73-82). Staining for extracellular antigens is performed directly after wash, while fixation and permeabilization is performed before staining for intracellular antigens, such as transcription factors and cytokines. For intracellular staining we are using commercially available reagents and protocols (BD and eBioscience)

- **Data acquisition:** Consistency of data acquisition will be ascertained by calibrating the flow cytometer with calibrating beads daily. For compensation of flow cytometry data we will prepare single stain controls with the appropriate antibodies (mainly using PBMCs, but commercially available compensation beads will be utilized for weakly expressed antigens), and perform compensation of fluorescent spillover with the compensation applications included in the flow cytometry analysis softwares DIVA (Becton Dickinson) and FlowJo (TreeStar). At least 10,000 cell events will be collected including appropriate isotype controls for cell surface markers and intracellular proteins. Viability dyes will be used to facilitate the gating of “live” cell populations.

- **Data analysis:** We will utilize standardized analysis and gating strategies for multi parametric flow-cytometry mAb panels (*Herzenberg LA et al. Nat Immunol 2006;7(7):681-5; Lugli E et al. Cytometry A 2010;77(7):705-713*). All samples will be analyzed by setting appropriate side and forward scatter gates to exclude cell clumps and debris, and to include the population of interest: lymphocytes. A “live” gate in the fluorescence channel containing the viability stain will be used to exclude dead cells. Fluorescence minus one (FMO, samples that include all antibodies but the one of interest) and isotype controls will be used to distinguish positive and negative populations for studied antigens. The results will be reported as percent of gated cells positive for each antibody. A BD FACSAria or BD LSR II flow cytometer with DIVA software (BD) will be used for data acquisition. The quantitative, continuously distributed data generated by this procedure will be analyzed using DIVA and/or FlowJo. Additional analysis with softwares for complex statistical and visual multivariable analysis, (available as freeware or at <https://www.cytobank.org/platform.html>) such as SPICE, bh-SNE and CITRUS will be performed to the best advantage. These novel and powerful analysis tools are especially suited for presentation of high-dimensional data sets, identifying rare biological subsets, and gating single-cell events across different samples (*Saeyns Y et al. Nat Rev Immunol 2016; 16:449-62*).

5. Analytical performance of the assay and the metrics to determine the level of the change following the treatment: These studies exploring T cell populations have been extensively studied in [name]’s laboratory. All samples are coded and assays are performed in blinded fashion. Assays are batched and contain both positive and negative biological controls. [name] laboratory routinely include PBMCs and BM mononuclear cells from healthy individuals as controls for all the flow-cytometry runs. The results from controls are stored and averaged to generate a range for normal individuals. In our analysis we are achieving a high reproducibility in measuring the effects of the treatment under investigation in regard to T cell subset(s) numbers and/or other measurable markers (co-signaling molecules, transcription factors, cytokines etc.) and the correlation between

repeated measurements from the same patients. Based on our performance analysis the correlation between repeatedly measured subsets is very high (>90%) with the lower bounds of the 95% confidence limits higher than 80% for majority of the markers measured, implying the high reproducibility of our assay. We have also developed criteria for measuring the magnitude of markers changes that take into the account differences between the baseline and post-treatment values (unpublished data). Specifically, for each marker, we modeled the log-scale percentage of cells expressing specific markers as a function of time and clinical effect. A linear mixed effects regression model with a random intercept for each patient was then used to estimate the differences between time points for each marker while accounting for the patient clustering. Standard linear regression models were used to estimate differences in log-scale percentages between patients at pre-treatment and healthy controls. For each marker and each model, we extracted the test statistic associated with the difference between time points (or groups) and plotted them using standard visualization approaches such as plots and heatmaps.

6. Clinical utility of the integrated assay: Flow values at each time point will be summarized using geometric means and standard deviation. Differences in baseline values between patient subgroups will be explored using linear regression models. We are specifically interested in determining what pretreatment signature is associated with outcome, such as having a complete response or becoming refractory. To this end, we will use logistic regression models with ROC analysis to describe which pretreatment parameters are potential predictors of outcomes following treatment. Values will be checked for skewness and log-transformed as appropriate. The change in flow values at each time point after blinatumomab and blinatumomab plus checkpoint inhibitor(s) relative to the baseline value will be modeled using mixed-effects, linear regression models that include fixed effects for time point and a random effect for the patient to account for within-patient correlation of measurements. Post-treatment changes in T cell populations will be correlated with clinical outcomes such as CR vs. No CR or MRD vs. No MRD using interaction tests. T cell subsets in the PB and BM defined by multicolor flow cytometry will be summarized before and after treatment with blinatumomab alone or plus checkpoint inhibitors by treatment group using summary statistics. Differences in T cells before and after treatment will be explored using non-parametric Wilcoxon signed rank tests or paired t tests as appropriate. The expression of co-inhibitory/-stimulatory molecules will also be examined in the same way.

References:

[figure not shown]
